1.3 Secondary Objectives

- To evaluate safety and toxicity, and quality of life scores
- To evaluate the time to the next surgery for a head and neck malignancy
- To estimate CFS from the time of study registration
- To estimate OS from the time of study registration
- To characterize distinct tumor and circulating immunophenotypes and correlate these findings with outcomes

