5.6 Duration of Follow-Up

Participants, regardless if they receive the full course of therapy, will be followed for best overall response and development of first invasive OSCC and for survival for 5 years from the time of study registration throughout the course of the trial. Participants removed from protocol therapy for unacceptable adverse event and if they have not developed first invasive OSCC at time of discontinuation of protocol therapy, will continue to be followed until first invasive OSCC and survival until death or 5 years from study registration (whichever occurs first).

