11.1.6 Cancer-Free Survival and Overall Survival

Overall Survival: Overall Survival (OS) is defined as the time from study registration to death due to any cause, or censored at date last known alive.

Cancer-Free Survival: Cancer-Free Survival (DFS) is defined as the time from study registration to development of invasive oral cancer or death due to any cause. Participants alive without disease progression or recurrence (of invasive oral cancer) are censored at date of last disease evaluation.

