11.1.7 Time to Next Surgery

Time to Next Surgery: Time to Next Surgery is defined as the time from the first study treatment to any head & neck surgery or resection for biopsy-proven carcinoma in situ (CIS) or invasive oral carcinoma (including all stages).

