13. STATISTICAL CONSIDERATIONS

The primary objective of this trial is to evaluate best overall response rate (CR+PR). A two-stage design (Simon's optimal design) will be used to minimize the number of patients enrolled. Sixteen eligible patients who start protocol treatment are to be accrued in the first stage. If there are ≤ 1 patients with disease in response, accrual to this trial will be closed with the expectation that there is little evidence that the response rate will reach 25%. The probability that the trial will close early is 51.5% if the true response rate is 10%. If there are >1 patients with disease in response, accrual will continue until a total of 33 eligible patients who start protocol treatment are entered. If there are > 5 patients with disease in response among 33 eligible patients who began protocol treatment, further testing of this regimen will be considered. If the true response rate is 25%, the probability of concluding the regimen is effective is 84.3%, if the true response rate is 10%, the probability of concluding the regimen is effective is 9.8%. Allowing for patients to be declared ineligible or to not start protocol treatment after registration, a total of 35 patients will be entered.

The primary efficacy population includes all eligible patients who begin protocol treatment. Best overall response will be summarized as a proportion with a corresponding exact 95% confidence interval (CI) (if the trial closes to accrual after the first stage), or a corresponding 95% (two-stage) CI if the trial closes to accrual after the second stage.

For secondary objectives:

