- Adverse events will be classified and graded according to the CTCAE v.5.0. Frequencies of adverse events will be summarized among patients who begin protocol therapy. The following stopping rule will be used to monitor excessive protocol related toxicity: if 3 or more of the first 10 patients who begin protocol treatment experience treatment related toxicities which cause extreme delays (protocol treatment needed to be stopped >10 weeks) or excessive treatment related toxicities, accrual to the trial will be suspended to further evaluate the events and decisions made regarding the overall status of the trial. If the true rate due to toxicity is 10% then the probability of suspending accrual is 7%; if the true rate is 20%, then the probability of suspending accrual is 32%; if the true delay rate is 30% then the probability of suspending accrual is 62%. Adverse events will be continuously monitored throughout the trial by the study team with decisions made accordingly regarding the study status and patient entry throughout the duration of the trial.

- The distributions of time-to-event endpoints will be estimated using the Kaplan-Meier method with corresponding 95% confidence intervals for the median or time-specific event time.
- Another endpoint is to assess quality of life (QOL). QOL will be assessed via self-report questionnaires at the timepoints outlined in the Study Calendar. Descriptive statistics from the questionnaires will be summarized across timepoints of assessment. Rates of drop-out/non-response to QOL assessments and corresponding reason will also be summarized across timepoints of assessment.
- Several correlative studies are also planned. Given the small sample size of this trial, these studies are exploratory. Samples will be collected at baseline and at post-baseline timepoints as outlined in the Study Calendar. Human immune cell markers (see 9.1 Biomarker Studies) from patients with evaluable tumor and peripheral blood samples will be summarized descriptively and graphically. Within subject changes in these markers will also be analyzed. Correlation between immune checkpoint receptor ligands and best overall response will be analyzed. Assuming 27 evaluable patients with baseline and a post-baseline value provides 80% power to detect .58 SD mean difference (Wilcoxon sign rank test two-sided 0.05 alpha level) in any given circulating or tumor immune marker.

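### Time to next surgery has no rule for death, so Kaplan-Meier censors deaths by default and tends to overstate the probability of surgery

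*Combined protocol and SAP*

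**What the plan says.** Time to next surgery is a secondary objective in Section 1.3: "To evaluate the time to the next surgery for a head and neck malignancy". Section 11.1.7 defines it: "Time to Next Surgery is defined as the time from the first study treatment to any head & neck surgery or resection", where the operation must be for biopsy-proven carcinoma in situ or invasive oral carcinoma. That definition does not mention death and has no censoring rule.

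Section 13 states the analysis for all such endpoints together: "The distributions of time-to-event endpoints will be estimated using the Kaplan-Meier method", and adds 95% intervals for either the median or an estimate at a given time. It makes no exception for time to next surgery and names no time point. The document mentions neither competing risks nor cumulative incidence.

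The two survival endpoints in Section 11.1.6 do deal with death. CFS is "defined as the time from study registration to development of invasive oral cancer or death due to any cause", and OS is "time from study registration to death due to any cause, or censored at date last known alive". Both have a censoring rule. Section 11.1.5 likewise counts death as an event, with a censoring rule, for the durations of overall and complete response.

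**The concern.** Kaplan-Meier assumes that a censored patient could still have the event later, at the same rate as those who remain under observation. That is reasonable for a patient whose follow-up has simply ended, but not for one who has died. If deaths are censored, one minus Kaplan-Meier estimates how often surgery would occur if nobody died first. The proportion of these patients who go on to surgery is a different quantity, and it is lower whenever deaths come before later surgeries.

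Death before surgery is plausible here. Section 2.1 puts the mean age at PVL diagnosis in the seventh decade, Section 3.1.5 admits ECOG 2, and follow-up runs to five years. Two of the four eligibility routes in Section 3.1.1 take patients for whom surgery is indicated but cannot be done or was refused. Some of them could develop cancer and die without resection.

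The study hypothesis in Section 1.1 includes a longer time to the next surgery. With a single arm, any reader who wants context will compare the estimate with outside surgery rates, so it should be a probability that applies to real patients.

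**Working it through.** The plan gives no event count, rate or power for time to next surgery, so there is no stated figure to reproduce. The check asks how far the two estimators differ under stated assumptions.

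**Inputs**

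- Horizon: t = 5 years. Section 5.6 follows patients "for survival for 5 years from the time of study registration". Section 13 names no time point, so five years is my choice.
- Surgery rate: h1 = 0.10 per year. This is an assumption that uses the annual transformation rate for oral PVL in Section 2.1 as a proxy.
- Rate of death before surgery: h2 is not in the documents. Assumed range: 0.01 to 0.05 per year.
- Sample size: n = 33, from Section 13: "accrual will continue until a total of 33 eligible patients who start protocol treatment are entered".

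**Formulas (constant rates)**

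- One minus Kaplan-Meier with deaths censored: 1 − exp(−h1·t)
- Cumulative incidence: h1/(h1+h2) × [1 − exp(−(h1+h2)·t)]
- Expected deaths before surgery: n × h2/(h1+h2) × [1 − exp(−(h1+h2)·t)]

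**Results at 5 years**

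One minus Kaplan-Meier is 1 − exp(−0.5) = 39.3% in every row.

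| h2 per year | Cumulative incidence | Excess of 1−KM (points) | Expected deaths before surgery, n = 33 |
|---|---|---|---|
| 0.01 | 0.909 × (1 − e^−0.55) = 38.5% | 0.9 | 1.3 |
| 0.02 | 0.833 × (1 − e^−0.60) = 37.6% | 1.7 | 2.5 |
| 0.03 | 0.769 × (1 − e^−0.65) = 36.8% | 2.6 | 3.6 |
| 0.05 | 0.667 × (1 − e^−0.75) = 35.2% | 4.2 | 5.8 |

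**Other surgery rates**

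- Reading 10% per year as a yearly probability gives h1 = −ln(0.9) = 0.105. One minus Kaplan-Meier is then 41.0%, against 40.0% to 36.6% for h2 of 0.01 to 0.05, an excess of 0.9 to 4.3 points.
- Section 2.1 also gives a mean transformation rate of 63.9% with mean follow-up of 7.4 years, so h1 = −ln(0.361)/7.4 = 0.138. One minus Kaplan-Meier is 49.8%, against 48.7% to 44.7%, an excess of 1.1 to 5.1 points.

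**Against sampling error**

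For a proportion of 39% in 33 patients with complete follow-up, the standard error is √(0.39 × 0.61/33) = 8.5 points. A simulation of 5,000 trials of 33 patients (h1 = 0.105, complete follow-up to five years) gave standard errors of 8.6, 8.4 and 8.4 points at h2 of 0.01, 0.02 and 0.05. The mean one-minus-Kaplan-Meier estimates were 41.2%, 41.0% and 40.9%, and the mean cumulative incidences 40.3%, 39.1% and 36.6%, in line with the formulas.

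**The median**

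At h1 = 0.10 the Kaplan-Meier median is ln(2)/0.10 = 6.9 years. At 0.138 it is 5.03 years. Both lie beyond five years of follow-up, so the practical issue is the time-specific estimate.

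**The case against.** The strongest reply is that this is a gap in wording with little consequence. The plan nowhere says that deaths are censored for this endpoint, so an analyst could still handle them properly. The endpoint is secondary and descriptive, and the decision on further testing depends on response alone. OS and CFS count deaths and are reported alongside. The excess is smaller than one standard error in every case above. Its direction makes surgery look more frequent, which works against the study hypothesis and cannot by itself produce a false claim of benefit.

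Most of that stands, and it is why the point is minor. It does not remove the point. Sections 11.1.7 and 13 followed as written lead to censoring of deaths, and the analyst has no other instruction. The discrepancy is systematic, so more patients would not reduce it.

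Four stronger readings are tempting, and the documents do not support them.

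- A reader might infer that the plan prescribes censoring at death. It does not. The censoring follows by default from the two sections.
- A reader might infer that the estimate is always too high. The two estimators agree if no death precedes a later observed surgery, and at a death rate of 0.01 per year only about 1.3 deaths before surgery are expected.
- A reader might spread the 40% mortality in Section 2.1 over 7.4 years, giving −ln(0.6)/7.4 = 0.069 per year and an excess of 5.6 points. But 7.4 years is the mean follow-up given with the transformation rate, not with the mortality figure. The calculation also puts every death before surgery, whereas Section 2.3 says that a cancer diagnosis leads to referral for resection.
- A reader might infer a biased reported median. Under the rates used here the median would usually not be reached within follow-up.

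**Conclusion.** The point holds as a minor one. Time to next surgery has neither a rule for death nor a censoring rule, and the planned Kaplan-Meier analysis then censors deaths before surgery by default. If such deaths precede later surgeries, the probability of surgery is overstated. The size is about 1 to 4 points at five years, assuming surgery at 0.10 per year and death before surgery at 0.01 to 0.05 per year, against a standard error of about 8 points. The direction is certain once such deaths occur. The size is not, because transformation in PVL stands in for surgery in a mixed population, the rates are taken as constant, and the documents give no rate of death before surgery. The primary endpoint, OS and CFS are unaffected.

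**What to change.** State in Sections 11.1.7 and 13 how death is handled for this endpoint. There are two sound options.

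1. Estimate time to next surgery by the cumulative incidence function (Aalen-Johansen), with death without surgery as the competing event.
2. Define surgery-free survival, with surgery or death as the event, and keep Kaplan-Meier.

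The first answers how often surgery occurs. The second answers how long patients live without it.

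Under either option, censor patients who are alive without surgery at the last date on which their surgery status is known. Censoring at the last oral examination would be a poor choice. After a first invasive cancer, the study calendar notes require only survival updates and leave photographs and measurements to discretion. Patients awaiting resection could therefore be censored just when surgery is most likely. For the same reason, confirm that surgery status is recorded at the survival contacts.

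The cost is a sentence or two in the plan and slightly more analysis work. Deaths are already recorded through survival follow-up, and the surgery date is needed whichever estimator is used.

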14. PUBLICATION PLAN

The results should be made public within 24 months of reaching the end of the study. The end of the study is the time point at which the last data items are to be reported, or after the outcome data are sufficiently mature for analysis, as defined in the section on Sample Size, Accrual Rate and Study Duration. If a report is planned to be published in a peer-reviewed journal, then that initial release may be an abstract that meets the requirements of the International Committee of Medical Journal Editors. A full report of the outcomes should be made public no later than three (3) years after the end of the study.

APPENDIX A PERFORMANCE STATUS CRITERIA

ECOG Performance Status Scale		Karnofsky Performance Scale	
Grade	Descriptions	Percent	Description
0	Normal activity. Fully active, able to carry on all pre-disease performance without restriction.	100	Normal, no complaints, no evidence of disease.
		90	Able to carry on normal activity; minor signs or symptoms of disease.
1	Symptoms, but ambulatory. Restricted in physically strenuous activity, but ambulatory and able to carry out work of a light or sedentary nature (e.g., light housework, office work).	80	Normal activity with effort; some signs or symptoms of disease.
		70	Cares for self, unable to carry on normal activity or to do active work.
2	In bed <50% of the time. Ambulatory and capable of all self-care, but unable to carry out any work activities. Up and about more than 50% of waking hours.	60	Requires occasional assistance, but is able to care for most of his/her needs.
		50	Requires considerable assistance and frequent medical care.
3	In bed >50% of the time. Capable of only limited self-care, confined to bed or chair more than 50% of waking hours.	40	Disabled, requires special care and assistance.
		30	Severely disabled, hospitalization indicated. Death not imminent.
4	100% bedridden. Completely disabled. Cannot carry on any self-care. Totally confined to bed or chair.	20	Very sick, hospitalization indicated. Death not imminent.
		10	Moribund, fatal processes progressing rapidly.
5	Dead.	0	Dead.

APPENDIX B GUIDANCE ON CONTRACEPTION

Highly Effective Methods of Contraception

Highly effective methods of contraception have a failure rate of < 1% when used consistently and correctly. WOCBP and female partners of male subjects, who are WOCBP, are expected to use one of the highly effective methods of contraception listed below. Male subjects must inform their female partners who are WOCBP of the contraceptive requirements of the protocol and are expected to adhere to using contraception with their partner.

At a minimum, subjects must agree to use one highly effective method of contraception as listed below:

For WOCBP

Highly effective methods of birth control include the following:

- Progestogen only hormonal contraception associated with inhibition of ovulation
- Hormonal methods of contraception including oral contraceptive pills (combination of estrogen and progesterone), vaginal ring, injectables, or implants
- Intrauterine devices (IUDs) (hormonal or non-hormonal)
- Intrauterine Hormone-releasing System (IUS)
- Bilateral tubal ligation
- Vasectomy
- Complete abstinence (complete avoidance of heterosexual intercourse)

For male subjects with partners that are WOCBP

- Condom

All male subjects who have partners who are WOCBP must use condoms as their second method of contraception.

[figure not shown]
Women of childbearing potential (WOCBP) receiving nivolumab will be instructed to adhere to contraception for a period of 5 months after the last dose of investigational product. Men receiving nivolumab and who are sexually active with WOCBP will be instructed to adhere to contraception for a period of 31 weeks after the last dose of investigational product. These durations have been calculated using the upper limit of the half-life for nivolumab (25 days) and are based on the protocol requirement that WOCBP use contraception for 5 half-lives plus 30 days and men who are sexually active with WOCBP use contraception for 5 half-lives plus 90 days after the last dose of nivolumab.

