macaques. In vitro assays have demonstrated the ability of nivolumab to potently enhance T-cell response and cytokine production (such as interferon alpha release); when later given to cynomolgus macaques at high concentrations, there were no adverse immune-related events, independent of circulating levels of anti-nivolumab antibodies [43]. In intravenous (IV) repeat-dose toxicology studies in cynomolgus macaques, nivolumab was well tolerated at doses up to 50 mg/kg, administered weekly for 5 weeks, and at doses up to 50 mg/kg, administered twice weekly for 27 doses.

The pharmacokinetics of nivolumab have been reported in human subjects over a dose range of 0.1 to 10 mg/kg administered as a single dose or as subsequent doses at 2 to 4 week intervals. The geometric mean (% CV%) clearance (CL) was 9.5 mL/h (49.7%), geometric mean volume of distribution at steady state (V_{ss}) was 8.0 L (30.4%), and geometric mean elimination half-life (t_{1/2}) was 26.7 days (101%). Steady-state concentrations of nivolumab were reached by 12 weeks when administered at 3 mg/kg every 2 weeks and systemic accumulation was approximately 3-fold. The exposure to nivolumab increased dose proportionally over the dose range of 0.1 to 10 mg/kg administered every 2 weeks. The clearance of nivolumab increased with increasing body weight. The population pharmacokinetic (PPK) analysis suggested that the following factors had no clinically meaningful effect on the clearance of nivolumab: age (29 to 87 years), gender, race, baseline LDH, and PD-L1 expression. Although patient performance status, baseline glomerular filtration rate (GFR), albumin, body weight, and mild hepatic impairment did have a mild effect on nivolumab clearance, the effect was not clinically meaningful [41]. Additionally, PPK and exposure response analyses have been performed to support the use of 240 mg IV flat dosing every 2 weeks and 480 mg IV flat dosing every 4 weeks in addition to the 3 mg/kg every 2 week regimen. Using the PPK model, exposure to nivolumab at 240 mg IV flat dose (every 2 weeks) or 480 mg IV flat dose (every 4 weeks) was identical to a dose of 3 mg/kg for subjects weighing 80 kg.

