3.1.4 Age 18 years or older

3.1.5 ECOG performance status ≤ 2 (Karnofsky $\geq 60\%$, see Appendix A)

3.1.6 Participant must have normal organ and marrow function as defined below within 21 days prior to study registration:

- leukocytes	$\geq 3,000/\text{mcL}$
- absolute neutrophil count	$\geq 1,000/\text{mcL}$
- platelets	$\geq 100,000/\text{mcL}$
- total bilirubin	$\leq 2.0 \text{ g/dL}$
- AST(SGOT)/ALT(SGPT)	$\leq 2.5 \times$ institutional upper limit of normal within normal institutional limits
- creatinine	

OR

- creatinine clearance	$\geq 60 \text{ mL/min}/1.73 \text{ m}^2$ for participants with creatinine levels above institutional normal
------------------------	--

3.1.7 Ability to understand and the willingness to sign a written informed consent document

3.1.8 Women of childbearing potential (WOCBP) must agree to use appropriate method(s) of contraception. WOCBP should plan to use an adequate method to avoid pregnancy for 5 months (30 days plus the time required for nivolumab to undergo five half-lives) after the last dose of investigational drug

3.1.9 Women of childbearing potential must have a negative serum or urine pregnancy test (minimum sensitivity 25 iu/l or equivalent units of hcg) at screening. Pregnancy test will be repeated on the day of the first dose of study drug (before administration), although results of this test are not required for registration.

“Women of childbearing potential (WOCBP)” is defined as any female who has experienced menarche and who has not undergone surgical sterilization (hysterectomy or bilateral oophorectomy) or who is not postmenopausal. Menopause is defined clinically as 12 months of amenorrhea in a woman over 45 in the absence of other biological or physiological causes. In addition, women under the age of 55 must have a documented serum follicle stimulating hormone (FSH) level greater than 40 mIU/mL

3.1.10 Men who are sexually active with WOCBP must agree to use any contraceptive method with a failure rate of less than 1% per year. Men who are sexually active with WOCBP will be instructed to adhere to contraception for a period of 7 months after the last dose of investigational product. Women who are not of childbearing potential (ie, who are postmenopausal or surgically sterile as well as azoospermic men) do not require contraception

See Appendix B for further guidance on contraception.

Exclusion Criteria

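### Appendix B bases the contraception periods on an upper-limit half-life of 25 days, below the 26.7-day geometric mean in Section 2.2.1.1, and men are given two different periods

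*Combined protocol and SAP*

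**What the plan says.** Appendix B gives a rule and an input. The rule for women of childbearing potential is that "WOCBP use contraception for 5 half-lives plus 30 days"; for men it is that "men who are sexually active with WOCBP use contraception for 5 half-lives plus 90 days after the last dose of nivolumab". The input is described as a bound: "These durations have been calculated using the upper limit of the half-life for nivolumab (25 days".

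From these, Appendix B derives two periods. Women "will be instructed to adhere to contraception for a period of 5 months after the last dose of investigational product", and men are to follow "contraception for a period of 31 weeks after the last dose of investigational product". Section 3.1.8 repeats the 5 months for women with the same rule. Section 3.1.10 instead tells men to follow "contraception for a period of 7 months after the last dose of investigational product". After that criterion the reader is sent to Appendix B for further guidance.

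The pharmacokinetic summary in Section 2.2.1.1 says of nivolumab that the "geometric mean elimination half-life (t_{1/2}) was 26.7 days (101", where 101 is the percentage coefficient of variation.

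**The concern.** The word that causes trouble is the label on the 25 days. A period built on an upper limit is meant to be conservative: it should cover participants who clear the drug slowly. Here the value called an upper limit is lower than the central value reported elsewhere in the protocol, for a quantity with very wide variation between subjects. Either the label is wrong, or the two figures come from different analyses and the protocol does not say so.

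At stake is an instruction given to participants to limit exposure in pregnancy. Its written justification conflicts with the protocol's own pharmacokinetics, and a site that reads both Section 3.1.10 and Appendix B finds two periods for men. The primary endpoint, the sample size and the analysis are not affected.

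**Working it through.** **Inputs.** Half-life 25 days (Appendix B). Geometric mean half-life 26.7 days, CV 101% (Section 2.2.1.1). Rule: 5 × half-life + 30 days for women, + 90 days for men (Appendix B; the women's rule also in Section 3.1.8). Stated periods: 5 months for women; 31 weeks (Appendix B) or 7 months (Section 3.1.10) for men. Assumption: one month is 365.25/12 = 30.44 days, so 5 months is 152.2 days and 7 months is 213.1 days. 31 weeks is 217 days.

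**Step 1: reproduce the plan at 25 days.**
- Women: 5 × 25 + 30 = 155 days = 5.09 months, stated as 5 months.
- Men: 5 × 25 + 90 = 215 days = 30.7 weeks = 7.06 months, stated as 31 weeks and as 7 months.

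The stated periods follow from the stated input, to rounding.

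**Step 2: the same rule at the reported mean, as an illustration.**
- Women: 5 × 26.7 + 30 = 133.5 + 30 = 163.5 days.
- Men: 5 × 26.7 + 90 = 133.5 + 90 = 223.5 days.

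| Stated period | Days | Minus rule at 25 d | Minus rule at 26.7 d | Longest half-life covered |
|---|---|---|---|---|
| Women, 5 months | 152.2 | −2.8 | −11.3 | (152.2 − 30)/5 = 24.4 d |
| Men, 31 weeks | 217 | +2.0 | −6.5 | (217 − 90)/5 = 25.4 d |
| Men, 7 months | 213.1 | −1.9 | −10.4 | (213.1 − 90)/5 = 24.6 d |

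With 30-day months (150 and 210 days), the 5- and 7-month periods are 5 days under the rule at 25 days and 13.5 days under it at 26.7 days.

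**Step 3: what is lost at 26.7 days.** Five half-lives take 133.5 days. Five months leaves 152.2 − 133.5 = 18.7 of the added 30 days. Thirty-one weeks leaves 83.5 of the added 90, and 7 months leaves 79.6. The five half-lives are covered in every case.

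**Step 4: could 25 days be an upper limit of the Section 2.2.1.1 quantity?** No, because it lies below that quantity's geometric mean. If half-life is taken as log-normal (an assumption) with a 101% CV, then σ = √ln(1 + 1.01²) = 0.839, and the share of subjects above 25 days is 1 − Φ(ln(25/26.7)/0.839) = 53%. On that assumption 25 days is near the middle of the distribution.

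**Step 5: sensitivity.** Each extra day of half-life adds 5 days to the rule. The document gives no upper limit for the half-life, so the gap at a true upper limit cannot be computed from it.

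**Step 6: the two male periods.** 217 − 213.1 = 3.9 days apart.

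**The case against.** A reader might infer that the protocol miscalculated, and that its periods fall short of its own rule. The documents do not support that. At the 25 days that Appendix B states, 31 weeks exceeds the rule by 2 days. Seven calendar months run from 212 to 215 days and so can equal it. Five calendar months run from 150 to 153 days, 2 to 5 days under. These are rounding differences. The gaps of 6.5 to 11 days appear only when 26.7 days is substituted, and that is a mean, whereas the rule as described calls for an upper limit. They are therefore neither the protocol's calculation nor a corrected one.

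A reader might also infer that the periods are wrong or that the washout fails. That too goes beyond the text. The two half-lives may come from different analyses: the Section 2.2.1.1 value is reported over 0.1 to 10 mg/kg, single and repeated dosing, and Appendix B gives no source for its 25 days. At 26.7 days only part of the added margin goes. Few women of childbearing potential may enroll, since Section 2.1 puts mean age at diagnosis of the main disease in the seventh decade. However, entry is open from age 18, and the male requirement depends on the partner.

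All of this limits the size of the point. It does not remove it: if the two figures describe different things, the protocol has to say so, and it does not.

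**Conclusion.** The point holds as an unreconciled input, not as an arithmetic error. A half-life of 25 days cannot be the upper limit of a quantity whose geometric mean is 26.7 days, and the document offers no explanation. The stated periods reproduce to rounding from 25 days. The illustrative difference at the reported mean is about 11 days for women, and 6.5 days (31 weeks) or about 10 days (7 months) for men. These figures rest on the protocol's own rule and an average month of 30.44 days. They would be larger at a true upper limit, for which the document gives no value. The mismatch of about 4 days between the two male periods stands whatever the half-life. This is modest in size but worth correcting, because a participant-safety instruction should not rest on a basis that the same document contradicts.

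**What to change.** Reconcile Section 2.2.1.1, Sections 3.1.8 and 3.1.10, and Appendix B:

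1. Give the source of the 25-day value and say what it represents, or correct either the value or its description as an upper limit.
2. Check the stated periods against the protocol's own rule using the reconciled half-life, and say how days are rounded to weeks or months.
3. State one male period, in one unit, in both Section 3.1.10 and Appendix B.

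The outcome may be a change of wording only or a change of period; which half-life or period is right is for the sponsor to determine. The cost is a wording amendment in these sections, plus matching changes to any participant-facing text that repeats the periods. No design or analysis element changes.
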